#### 4.6.1 Baseline Variables

Baseline variables will be collected including but not limited to: gender, race, age, BMI, hypertension, heart disease, diabetes, smoking status, previous stroke history, baseline rupture/un-rupture status,

## **SAfety and Effectiveness of the Treatment of Wide Neck, Saccular Intracranial Aneurysms with the Neuroform Atlas™ Stent System**

### **Short Study Name: ATLAS**

aneurysm size, dome size, neck size, dome to neck ratio, aneurysm location, use of antiplatelet agents, and other factors. For baseline ruptured aneurysms, the days/time from the most recent rupture to the index procedure will be summarized and reported. For unruptured aneurysms measuring <7mm for each of three dimensions assessed (height, width, and depth), a baseline variable of “reason for treatment” will also be collected.

The baseline variables will be summarized using descriptive statistics. Continuous variables such as age and BMI will be summarized using mean, standard deviation and N. Categorical variables such as hypertension and diabetes will be summarized using a percentage of subjects exhibiting the characteristic along with the numerator and denominator of that percentage.

#### **4.6.2 Post-procedure Variables**

Stryker Neurovascular will analyze the success rate of the Neuroform Atlas™ Stent post-procedure with 95% CI. Stryker Neurovascular will also report any device malfunctions, and all available post procedure clinical outcomes as well as the immediate post procedure image score (Raymond score by Core Lab reading).

#### **4.6.3 Long Term Follow-up Variables**

Long-term safety data will be collected from 12 months through 3 years ( $\pm$  6 months) post-index procedure within the following categories:

- Neurological death or major ipsilateral stroke
- Any ischemic or hemorrhagic event of any severity or duration (including TIAs, SAH, and aneurysm rupture)
- Device-related SAEs

In addition, neurological assessments will be conducted in person at each follow-up visit, and all new and ongoing adverse events will be recorded and adjudicated as specified by the CEC charter.

For imaging performed per standard of care, the long-term effectiveness endpoints identified below will be assessed from 12 months through 3 years ( $\pm$  6 months) post-index procedure per the long-term follow-up schedule requirements:

- Retreatment
- Parent artery stenosis at the target aneurysm location (>50% stenosis)
- Composite effectiveness measure (complete aneurysm occlusion [Raymond 1] without significant parent artery stenosis at the target aneurysm location [>50% stenosis] or retreatment)
- Recanalization
- Stent migration based on follow-up angiogram
- Aneurysm occlusion of Raymond Class 1, 2, or 3
- Aneurysm occlusion of Raymond Class 1 and 2 combined
- Progressive occlusion of the target aneurysm

#### **4.6.4 Pooling across Institutions**

Subgroup analysis will be done to assess if there is heterogeneity among the sites, and to determine if pooling of the data is reasonable. The percentage of patients with total occlusion within each site will be determined and a Pearson chi-square statistic will be used to determine if there are differences between sites. If the p-value of the Pearson chi-square statistic is greater than 0.10 then the sites will be considered poolable. If there are one or two outlier sites, a sensitivity analysis will be done by including them in the analysis as well as excluding those sites in the repeat comparable analysis.

# **SAfety and Effectiveness of the Treatment of Wide Neck, Saccular Intracranial Aneurysms with the Neuroform Atlas™ Stent System**

## **Short Study Name: ATLAS**

### **4.6.5 Additional Comparisons**

There is no plan for any additional comparisons at this time.

### **4.6.6 Other Analysis Methods**

Stryker Neurovascular may carry out additional analyses for exploratory purposes, such as using the following variables as the stratified variable for additional subgroup analysis: gender, race and other baseline characteristics.

### **4.6.7 Covariates**

Baseline variables are mentioned in **Section 4.6.1** above. Additional procedural variables will be the length of the procedure, the number of coils successfully implanted, packing density, etc. Post procedure variables have been described in **Section 4.6.2**.

These additional covariates will be summarized using descriptive statistics as described for the baseline variables.

## **4.7 Subject Accountability**

All subjects will be included in a summary of subject accountability for this study. The frequency and percentages of subjects enrolled, present at each visit, discontinuing before study completion (including reason for discontinuation) and completing the study will be presented in the final report. For subjects lost to follow-up, the date of last contact will be used to define the censor date.

## **4.8 Follow-up and Reporting**

All subjects enrolled and devices used in the clinical investigation will be accounted for in the final report. All reasons for exclusion from analysis will be documented. Similarly, for all subjects and devices included in an analysis population, the measurements of all important variables will be accounted for at all relevant time points.

Subjects lost to follow-up or withdrawn from the study will be identified, and a descriptive analysis of them will be provided, including the reasons for their loss to follow-up and known treatment outcomes.

All PAS mITT subjects will be asked to return for a 2-year visit and a 3-year visit. If the 3-year visit window has elapsed at the initiation of the PAS follow-up, subjects will be asked to return for at least one long-term follow-up visit.

The analysis of long-term safety and effectiveness data will be descriptive only, as no formal hypotheses will be tested based on data collected during this phase of the study. Survival analysis will be used to estimate the incidence of specified safety endpoint events, as well as retreatment of the target aneurysm.

## **4.9 Assessment of Attrition Bias**

Differential attrition rates among subgroups of the ATLAS subjects could potentially bias the observed safety and durability status in both directions. Adverse events may prevent patients from adequately participating in the study, i.e., informative censorings are created. On the other hand, certain tests may be biased due to the under-participation of the healthier subgroup. Adverse events may result in more frequent hospital visits and therefore a better chance to report mRS and NIHSS. Difficult-to-treat aneurysms with suboptimal occlusion status may be more likely to undergo additional angiograms and to be evaluated with the Raymond-Roy scale.

Analyses will be performed at various stages of the PAS to evaluate the potential effects of attrition bias. Since subjects who died, withdrew, or are lost to follow-up can no longer be followed in the PAS, statistics reported for the PAS mITT cohort should be interpreted as conditional on a given subject's

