# Safety and Effectiveness of the Treatment of Wide Neck, Saccular Intracranial Aneurysms with the Neuroform Atlas™ Stent System

## Short Study Name: ATLAS

**Table 2 - Study Event Schedule through PAS Follow-up**

	ATLAS IDE Event Schedule						ATLAS PAS Event Schedule £		
	Pre-Implant	Implant / Procedural	Post-Implant †	2 Months (60d) ± 1 month	6 Months (180d) ± 1 month	12 Months (365d) ± 2 months	2 Years (730d) ± 6 months	3 Years (1095d) ± 6 months	Post 3-Years (43 – 60 months) ††
Medical History	X								
Neurological Exam*	X					X	X ∞	X ∞	X ∞
mRS†	X		X	X	X	X	X ∞	X ∞	X ∞
NIHSS*/**	X			±/-**	±/-**	X	X ∞	X ∞	X ∞
Hunt and Hess*/***	X		X			X	X ∞	X ∞	X ∞
Angiography****	X **** (MRA, CTA or DSA)	X (DSA)		+/-**** (MRA or DSA, per institution standards)	+/-**** (MRA or DSA, per institution standards)	X (DSA)	+/-**** (MRA, CTA, or DSA, per institution standards)	+/-**** (MRA, CTA, or DSA, per institution standards)	+/-**** (MRA, CTA, or DSA, per institution standards)
Adverse Event	X	X	X	X	X	X	X ∞	X ∞	X ∞
Antiplatelet	X		X	X	X	X	X	X	X
Quality of Life	X					X			

† Assessments must be performed within 72 hours after implant procedures, and prior to hospital discharge.

†† Post 3-year visits are required only for those subjects whose index procedure took place ≥ 43 months and ≤ 60 months prior to their enrollment into the PAS phase of the study.

\* At each Clinical Trial Site, a non-treating physician (or an appropriately trained/qualified designee) will be responsible for performing neurological examinations and/or performing assessments using neurologic rating/grading scales (mRS, NIHSS, Hunt and Hess). In addition, a neurological examination and/or an assessment using a neurologic rating/grading scale may be performed at any point in time if it is appropriate to do so, or in the case of a new neurological event.

\*\* The NIHSS is required at baseline and at 12 months of follow-up. In addition, the NIHSS is required at the 2- and 6-month follow-up visit and at any unscheduled visit if the subject's mRS score is > 0 in association with an adverse neurological event.

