**Short Study Name: ATLAS**

**Table 7 – Endpoint Measure Definitions in the Post-approval Study**

	Survival Analysis		Incidence Rate		% Subjects who Experienced the Outcome [2]			
	Competing Risk [1]	Event	Numerator	Denominator	Numerator	Denominator		
Primary Safety Outcome	Non-neurologic death	Death	Number of events (N1)	Person-time based on follow-up date (D1)	Number of subjects who experienced new outcome in the interval (N2)	Number of subjects present for one or more visits during or after the interval or experienced outcomes during the interval (D2)		
Neurological death								
New or worsening major ipsilateral stroke								
Any ischemic or hemorrhagic AE(s)								
Hemorrhagic Stroke								
Ischemic Stroke								
SAH								
Aneurysm Rupture								
TIA								
Device-related SAE(s)								
Grade 1 Raymond class in the absence of retreatment, or parent artery stenosis (>50%) at the target location	N/A	N/A	N/A	N/A	Number of subjects who are not retreated and whose current DSA met the outcome definition	Number of subjects with valid DSA or underwent retreatment		
Retreatment	Death	The first event	N1	D1	N2	D2		
Raymond Class	N/A	N/A	N/A	N/A	Number of subjects whose current DSA met the outcome definition	Number of subjects with valid DSA		
Parent Artery Stenosis > 50%	N/A	N/A	N/A	N/A				
Recanalization	Death	The first event	N1	Person-time based on DSA date				
Stent Migration								
Progressive Occlusion of the Target Aneurysm	N/A	N/A	N/A	N/A				

[1] Subjects are censored on the date of the event; other censoring events include lost-to-follow-up, consent withdrawal, and study early discontinuations due to other reasons.

[2] Repeated for each visit interval, i.e. 2-year, 3-year, post-3-year intervals.

[3] The observational period for the survival analysis and incidence rate starts on the day after a subject's 12-month follow-up visit.

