# **Safety and Effectiveness of the Treatment of Wide Neck, Saccular Intracranial Aneurysms with the Neuroform Atlas™ Stent System**

## **Short Study Name: ATLAS**

survival of the first 12 months after the procedure. At the initiation of the PAS, summary statistics on demographics and key clinical characteristics at 12-month follow-up visits will be compared between cohorts with and without deaths, withdrawals, and loss to follow-up. Once patient enrollment for the PAS begins, we will update the PAS mITT cohort with the actual enrollment and present the updated comparison in the interim progress reports and final report.. Sensitivity analyses will be carried out based on different assumptions of the pattern of loss to follow-up. Raymond-Roy scale and mRS will be reported within the context of previous test results. All analyses performed on the PAS mITT cohort will be compared to the PAS ITT population.

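### Section 4.9 recognises selective long-term imaging, but no planned check compares imaged with non-imaged retained subjects or adjusts for 12-month Raymond class, so the Table 7 imaging proportions may be biased

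*Combined protocol and SAP*

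**What the plan says.** Section 4.6.3 makes long-term effectiveness depend on routine imaging: "For imaging performed per standard of care, the long-term effectiveness endpoints identified below will be assessed from 12 months through 3 years". Table 2 leaves both the imaging and its type at 2 and 3 years to the site ("MRA, CTA, or DSA, per institution standards").

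For Raymond class and stenosis above 50%, Table 7 uses the denominator "Number of subjects with valid DSA". For the composite of Raymond 1 without retreatment or stenosis it uses "Number of subjects with valid DSA or underwent retreatment". No weighting or standardisation is given.

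Section 4.9 names the selection problem: "Difficult-to-treat aneurysms with suboptimal occlusion status may be more likely to undergo additional angiograms and to be evaluated with the Raymond-Roy scale". It then plans four things:

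- 12-month characteristics "will be compared between cohorts with and without deaths, withdrawals, and loss to follow-up";
- a set of sensitivity analyses: "Sensitivity analyses will be carried out based on different assumptions of the pattern of loss to follow-up";
- Raymond-Roy and mRS results reported in the light of earlier results, with no method stated;
- PAS mITT results compared with PAS ITT results.

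Sections 4.6 and 4.8 state that the long-term analysis is descriptive, with no formal hypotheses.

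**The concern.** Dropping out and not being imaged are different kinds of missing data. A subject who attends every long-term visit but has no angiogram is retained, yet is absent from the Table 7 occlusion denominator. If the chance of imaging depends on how well the aneurysm was occluded, the imaged group has a different case mix from the implanted group, and checks built on retention cannot show it.

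Durability of occlusion through 3 years is a stated long-term objective (Section 2.3.3). A fall in the Raymond 1 proportion between 12 months and 3 years could then reflect who was imaged rather than what happened to the aneurysms, and the planned output would not let a reader tell these apart.

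**Working it through.** **What each planned check can detect.** Take the case with no deaths, withdrawals or losses, in which well-occluded aneurysms are imaged less often.

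1. Dropout comparison: there is no dropout group, so nothing is found.
2. Loss-to-follow-up sensitivity analyses: there is no loss to vary, so nothing changes.
3. PAS mITT against PAS ITT: under Section 4.4 the two populations differ only by retention, so here they coincide. Even with dropout, a subject without a DSA in the interval enters the occlusion denominator of neither.
4. Reporting in the context of previous results: this could show the earlier class of imaged subjects. It commits neither to a comparison with non-imaged subjects nor to an adjusted rate.

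**Size.** The documents state no long-term occlusion rate or share imaged, so there is no figure to reproduce. The following is an illustration.

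Inputs:

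- Raymond 1 at 12 months: 62%. This is the planning rate in Section 4.2 for the composite effectiveness endpoint, used here as a stand-in for Raymond 1.
- Raymond 1 at 3 years: 95% if Raymond 1 at 12 months, 25% otherwise (assumed).
- Share imaged: i1 of those in Raymond 1 at 12 months, i2 of the rest (assumed).

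True rate = 0.62 × 0.95 + 0.38 × 0.25 = 0.589 + 0.095 = 68.4%.

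Crude rate = (0.62 × i1 × 0.95 + 0.38 × i2 × 0.25) / (0.62 × i1 + 0.38 × i2).

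| i1 | i2 | Numerator / denominator | Crude rate | Shift (points) |
|---|---|---|---|---|
| 50% | 60% | 0.3515 / 0.538 | 65.3% | −3.1 |
| 40% | 60% | 0.2926 / 0.476 | 61.5% | −6.9 |
| 40% | 80% | 0.3116 / 0.552 | 56.4% | −12.0 |

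With equal imaging the shift is zero.

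Changing the second conditional rate from 25% to 35% gives a true rate of 0.589 + 0.133 = 72.2%. The crude rate is then 66.3% with imaging at 50% and 75% (−5.9), and 62.0% at 40% and 80% (−10.2). The direction holds and the size moves modestly.

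**What standardising does.** Weight each 12-month class by its share among all implanted subjects with a 12-month DSA, and apply the 3-year rate seen in the imaged members of that class: 0.62 × 0.95 + 0.38 × 0.25 = 68.4% in every row. This recovery follows from the assumption that imaging depends only on 12-month class.

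**The case against.** A reader might infer that Section 4.9 compares only dropouts with non-dropouts, or that the long-term rates are certain to be biased and go wholly unchecked. The documents support neither reading. Section 4.9 plans three further items besides the dropout comparison, and the one on previous results bears on this very outcome. Because a 12-month DSA is required for all subjects (Section 3.10), an earlier Core Lab class should usually be available to report alongside a later one. Section 4.8 also promises that reasons for exclusion are documented and important variables accounted for over time. Section 4.9 says only that selective imaging may occur, and it refers to suboptimal occlusion without tying this to the 12-month reading. All of that stands. What remains is that the one relevant item has no stated method and need not cover subjects who were not imaged.

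Nor is every durability measure affected alike. Retreatment uses person-time and visit-based denominators rather than imaging. Recanalization also receives survival and incidence analyses, though these still depend on DSA.

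One could look to the imputation in Section 4.3. It does not mention long-term imaging, and the valid-DSA denominators in Table 7 leave no place for imputed results.

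It can also be said that the bias works against the device. That is so for Raymond 1, but not necessarily for every outcome. Under the same assumptions, and if progressive occlusion shares the valid-DSA denominator, progression to Raymond 1 would be 0.38 × 0.25 = 9.5% in truth. It would appear as 0.057 / 0.476 = 12.0% with imaging at 40% and 60%.

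Finally, weighting on many variables could be unstable. Of 153 evaluable subjects, 38% is about 58. With 60% imaged, about 35 remain across Raymond 2 and 3. This is a good reason to keep the adjustment simple.

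**Conclusion.** The gap is real but limited. The plan identifies selective imaging and specifies no analysis that compares imaged with non-imaged retained subjects or adjusts the proportions for 12-month class. The Table 7 occlusion and stenosis proportions may be biased as a result, even with complete retention.

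For Raymond 1 the named mechanism points downward. The illustrative shift is about −3 to −12 points, for imaging ratios (i2/i1) of 1.2 to 2.0. It rests on assumed imaging shares and assumed conditional 3-year rates, and on treating the 62% planning rate as a Raymond 1 rate. It is not an estimate of the bias in this trial.

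The primary endpoint, read from the required 12-month DSA, is untouched, and the long-term phase tests no hypothesis. The change is worth making because durability is the question that phase is meant to answer.

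**What to change.** In Section 4.9, add two items.

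1. For each PAS interval, tabulate imaged against not-imaged retained subjects by 12-month Core Lab Raymond class, and also by 12-month stenosis, retreatment and circulation.
2. Beside each crude Table 7 imaging proportion, report as a sensitivity estimate the rate standardised to the 12-month Raymond-class distribution of implanted subjects with a 12-month DSA. Collapse classes 2 and 3 if sparse, and give a bootstrap interval. State the assumption that imaging depends only on 12-month class. Imaging prompted by later symptoms or findings would break it, so the standardised rate supplements the crude one and does not replace it.

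The cost is some SAP wording, a little more analysis and wider intervals for the standardised rates. No new images or visits are needed.

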# **Safety and Effectiveness of the Treatment of Wide Neck, Saccular Intracranial Aneurysms with the Neuroform Atlas™ Stent System**

## **Short Study Name: ATLAS**

survival of the first 12 months after the procedure. At the initiation of the PAS, summary statistics on demographics and key clinical characteristics at 12-month follow-up visits will be compared between cohorts with and without deaths, withdrawals, and loss to follow-up. Once patient enrollment for the PAS begins, we will update the PAS mITT cohort with the actual enrollment and present the updated comparison in the interim progress reports and final report.. Sensitivity analyses will be carried out based on different assumptions of the pattern of loss to follow-up. Raymond-Roy scale and mRS will be reported within the context of previous test results. All analyses performed on the PAS mITT cohort will be compared to the PAS ITT population.

## **5 Data Management**

### **5.1 Data Collection and Processing**

Subject data will be collected in a secure electronic data capture (EDC) system via the Internet. The Principal Investigator or Sub-investigator must ensure the accuracy and completeness of the recorded data and then provide his/her electronic signature on the appropriate electronic Case Report Forms (eCRFs). Changes to data previously submitted to the Sponsor will require a new electronic signature by the investigator to acknowledge/approve the changes.

Visual and/or computer data review will be performed to identify possible data discrepancies. Manual and/or automatic queries will be created in the EDC system and will be issued to the site or angiographic Core Lab for appropriate response. The site staff will be responsible for resolving all queries in the database.

Results from the angiographic Core Lab will also be entered or uploaded into the EDC system. Audits may be performed for quality assurance of data handling against Core Lab procedures.

## **6 Adverse Events**

An Adverse Event (AE) is any undesired clinical response or complication experienced by a subject. All AEs (within the study duration), whether device-related or not, will be recorded on the AE case report forms. Data to be collected will include the description of the AE event term, onset and resolution dates (or whether the AE is ongoing), severity, management/treatment, outcome, and determination of the relationship to the device and/or procedure.

### **6.1 Adverse Event Definitions and Classification**

**Table 8 – Adverse Event Definitions and Classifications**

Term	Definition	Reference
Adverse Event (AE)	
Any untoward medical occurrence, unintended disease or injury, or untoward clinical signs (including abnormal laboratory findings) in subjects, users or other persons, whether or not related to the investigational medical device.
 
NOTE 1: This definition includes events related to the investigational medical device or procedures involved.
	ISO 14155

**Safety and Effectiveness of the Treatment of Wide Neck, Saccular Intracranial Aneurysms with the Neuroform Atlas™ Stent System**

**Short Study Name: ATLAS**

Term	Definition	Reference
Adverse Device Effect (ADE)	
Adverse event related to the use of an investigational medical device.
 
NOTE 1: This definition includes adverse events resulting from insufficient or inadequate instructions for use, deployment, implantation, installation, or operation, or any malfunction of the investigational medical device.
 
NOTE 2: This definition includes any event resulting from use error or from intentional misuse of the investigational device.
	ISO 14155
Serious Adverse Event (SAE)	
Adverse event that:
 
 
A. led to death,
 
B. led to serious deterioration in the health of the subject, that resulted in either: 
 
1. a life-threatening illness or injury,
 
2. a permanent impairment of a body structure or a body function,
 
3. in-subject or prolonged hospitalization,
 
4. medical or surgical intervention to prevent life-threatening illness or injury or permanent impairment to a body structure or a body function,
 
 
 
C. led to fetal distress, fetal death or a congenital abnormality or birth defect.
 
 
NOTE: Planned hospitalization for a pre-existing condition, or a procedure required by the clinical investigational plan, without serious deterioration in health, is not considered a SAE.
	ISO 14155
Serious Adverse Device Effect (SADE)	Adverse device effect that has resulted in any of the consequences characteristic of a serious adverse event.	ISO 14155
Unanticipated Adverse Device Effect (UADE)	Any serious adverse effect on health or safety or any life-threatening problem or death caused by, or associated with a device, if that effect, problem, or death was not previously identified in nature, severity, or degree of incidence in the investigational plan or application (including a supplementary plan or application), or any other unanticipated serious problem associated with a device that relates to the rights, safety, or welfare of subjects.	21 CFR Part 812

Underlying diseases are not reported as Adverse Events (AEs) unless there is an increase in severity or frequency during the course of the investigation. Death should not be recorded as an adverse event, but should only be reflected as an outcome to another specific SAE. Any AE experienced by the study

